8.4. Protocol Deviations

The list of protocol deviations will be compiled prior to database lock. All deviations will be reviewed and decisions for handling each of the deviations will be made prior to the start of data analysis.

8.5. Interim Analysis

Two interim analyses will be performed at 34% and 67% completion, testing for early efficacy or futility, using t-score boundaries that follow O’Brien-Fleming Analog alpha and beta spending rules. Assuming that the two interim analyses will occur after approximately 40 (1/3 of 119 total target areas) and 80 (2/3) target

areas have been assessed and adjudicated, the nominal alpha levels to reject the null hypotheses for efficacy are as follows in the table below.

Analysis Order	Number of Target Areas	Nominal critical point (Z-value)	Alpha level
1	40	-4.42	0.00000
2	80	-3.09	0.00122
Final	119	- 2.406	0.00804

Futility analyses are planned to be conducted to coincide in timing with the tentative interim analyses. The formal criterion for determination of futility is that at each interim look, if the condition power (defined as the probability of rejecting the null hypothesis at the final analysis given the data accumulated so far and under the assumption that the alternative hypothesis under the original design is true) falls below 20%, then the trial will be considered for stopping.

An interim monitoring tool, the most current version of PASS software will be used to estimate the conditional power.

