- Individuals who have evidence of one or more of the following skin fold conditions: erythema, maceration, denudation, satellite lesions, pain, itching, burning, moisture, and odor.
- Individuals whose treatment plan permits assessment of the skin fold condition(s) for up to six days.

Exclusion criteria

Individuals who meet any of the following criteria will not be eligible to participate in this study:

- Individuals whose target area(s) are being managed with topical treatments such as antibiotics, antifungals, ointments including skin protectants, anti-itch products, anoperineal dressings or absorbent pads (eg, ARD®).
- Individuals with a known allergy or sensitivity to the ingredients in the SPT, such as the fabric or H₂O₂, as well as the tape that may be used to secure the SPT.
- Individuals who are pregnant or are breastfeeding.

Description of Sites/Facilities At least one acute care facility (non-intensive care unit [non-ICU]) will be involved in the study. If more than one facility is involved, enrollment will be competitive.

Enrolling Participants: Up to six days.

Participant Duration: Up to six days.

Note:

Two interim analyses will be conducted to confirm that participants being enrolled present a balanced distribution of skin fold conditions.

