8. STATISTICAL CONSIDERATIONS

8.1. Sample Size Determination

The sample size of 119 skin fold conditions was selected to detect a minimal clinically significant difference of 10 in the VAS pain scale between days of SPT changes with an estimated standard deviation of 30 and a Bonferroni adjusted α of $\alpha = .0083$ at 80% power, using the “Paired Wilcoxon Signed-Rank Test” procedure in PASS 2021 Power Analysis and Sample Size Software (2021). NCSS, LLC. Kaysville, Utah, USA, ncss.com/software/pass). It is noted that participants may have skin folds with independent skin fold conditions. One participant may be the source of, at most, two skin fold conditions for the purposes of this study. The candidate skin fold conditions must be, in the assessment of the PI or qualified designee, anatomically distant enough to permit objective assessment of discomfort (pain, itching, and burning) in each target area by the participant. In the event that a participant withdraws from the study, additional participants will be enrolled to achieve a final number of 119 target areas with complete data and until adequate power for analysis has been reached.

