8.9. Statistical Analysis

Statistical analyses will be conducted in SAS[®] software, Version 9.4 or higher of the SAS System for Windows (Copyright © 2013 SAS Institute Inc.) or other appropriate statistical software. A p-value of $P < .05$ will be considered statistically significant.

All continuous variables will be summarized using the following descriptive statistics: (non-missing sample size), mean, standard deviation, median, maximum and minimum. The frequency and percentages (based on the non-missing sample size) of observed levels will be reported for all categorical measures. In addition, 95% confidence intervals will be calculated for all means.

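### The look-2 critical value and alpha in the Section 8.5 table disagree as printed, the scale and sidedness of the boundaries are left open, and the Synopsis gives the interim looks a different purpose

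*Combined protocol and SAP*

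**What the plan says.** **Section 8.1** sizes the study at 119. The target effect is given as "minimal clinically significant difference of 10 in the VAS pain scale between days of SPT changes with an estimated standard deviation of 30". The other inputs are a Bonferroni-adjusted alpha of .0083, 80% power and the paired Wilcoxon signed-rank procedure in PASS. The section does not say whether .0083 is one- or two-sided.

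**Section 8.5** gives the timing as follows: "Two interim analyses will be performed at 34% and 67% completion". The stated purpose of the looks is "testing for early efficacy or futility". The boundaries are described by the phrase "using t-score boundaries that follow", and the rule named is O'Brien-Fleming-type spending of both alpha and beta. The section then says that "the nominal alpha levels to reject the null hypotheses for efficacy are as follows in the table below". The heading of the critical-value column begins "Nominal critical point (Z-value". The printed rows are:

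| Look | Target areas | Critical point | Alpha |
|---|---|---|---|
| 1 | 40 | -4.42 | 0.00000 |
| 2 | 80 | -3.09 | 0.00122 |
| Final | 119 | -2.406 | 0.00804 |

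The section adds a futility criterion: stopping is considered if conditional power under the design alternative is below 20%.

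**Synopsis (1.1), closing note**: "Two interim analyses will be conducted to confirm that participants being enrolled present a balanced distribution of skin fold conditions". It mentions neither efficacy nor futility.

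**Section 8.9** says that a p-value below .05 "will be considered statistically significant", with no pointer to the final level in Section 8.5.

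**The concern.** The table is the decision rule for the interim and final tests, so each row should define one threshold. At look 2 the two columns define different ones: a result between them rejects by the alpha column and not by the critical-value column. Naming t in the text and Z in the table adds a second ambiguity about the scale.

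Sidedness matters more. It decides how much error the boundaries spend in total, and it should be the same in the sample size and in the stopping rule. If it is settled only after data have been seen, the success criterion becomes a data-dependent choice.

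Finally, someone who reads only the Synopsis would not learn that the looks test efficacy and futility or that the trial may stop early.

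**Working it through.** **Inputs.** Alpha .0083, difference 10, SD 30, 80% power and N = 119 (Section 8.1); looks at 40, 80 and 119 target areas, described as thirds, with the printed critical points and alphas (Section 8.5). Assumed: t degrees of freedom n - 1 = 39, 79, 118; SD 30 is the SD of the paired difference; target areas are independent.

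**1. Tail areas of the printed critical points.**

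| Look | Printed Z | Normal, one-sided | Normal, two-sided | t, one-sided | Printed alpha |
|---|---|---|---|---|---|
| 1 | -4.42 | 0.0000049 | 0.0000099 | 0.000038 | 0.00000 |
| 2 | -3.09 | 0.00100 | 0.00200 | 0.00138 | 0.00122 |
| Final | -2.406 | 0.00806 | 0.01613 | 0.00884 | 0.00804 |

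To five decimals, look 1 agrees only with the one-sided normal tail (two-sided would print 0.00001, t would print 0.00004). The final row fits the same scale to within 0.00002, which is immaterial. Look 2 fits no scale. Rounding does not explain it: Z from 3.085 to 3.095 gives 0.00102 to 0.00098. Inverting 0.00122 gives Z = 3.031.

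**2. What the spending rule gives.** The O'Brien-Fleming-type function is a(t) = 2[1 - Phi(z/sqrt(t))], with z the upper .0083/2 point, 2.640. At t = 1/3 and 2/3 the cumulative spend is 0.0000048 and 0.001226. Solving for the bounds by numerical integration, efficacy stopping only:

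- .0083 in one tail, exact thirds: 4.42, 3.03, 2.413; nominal p at look 2 is 0.00122.
- .00415 in each tail, exact thirds: 4.83, 3.32, 2.65.

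The first set reproduces the printed look-1 critical point and the look-2 alpha. The second does not fit the table. So -3.09 is the likely wrong entry, and the table is a one-sided .0083 table on the Z scale.

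**3. The final row.** The 2.413 above ignores futility. If the 20% conditional-power rule is treated as binding, with efficacy bounds 4.42 and 3.03 and a standardised drift of 3.24 to 3.55, the final bound that holds one-sided .0083 is 2.402 to 2.407. The printed -2.406 lies in that range.

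**4. Which sidedness reproduces 119.** A paired t-test with delta/SD = 10/30 at 80% power (noncentral t), multiplied by pi/3 for the Wilcoxon test:

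- two-sided .0083: 113 x pi/3 = 118.3, so 119;
- one-sided .0083: 98 x pi/3 = 102.6, so about 103.

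At 119, fixed-design power is about 80% two-sided and 87% one-sided.

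**5. Size of the look-2 discrepancy.**

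- One-tail error with futility ignored: 4.42/3.09/2.406 gives 0.0084; changing only look 2 to 3.03 gives 0.0084 to 0.0085. With 3.03 and binding futility as in step 3, it is 0.0082 to 0.0083.
- Chance that the look-2 Z falls between -3.03 and -3.09 under the null: 0.00122 - 0.00100 = 0.0002.
- The same chance under the sizing alternative: drift (10/30) x sqrt(119 x 3/pi) = 3.55; mean Z at look 2 in absolute value is 3.55 x sqrt(80/119) = 2.91; Phi(3.09 - 2.91) - Phi(3.03 - 2.91) is about 0.024 (0.027 by simulation of the signed-rank test).
- Of the simulated trials in that gap, about 1% then miss -2.406 at 119. The usual consequence is a decision delayed by 119 - 80 = 39 target areas.

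**6. Purpose of the looks.** The Synopsis note gives a check on the mix of skin fold conditions. Section 8.5 gives efficacy and futility tests with possible stopping. Both are current text, and neither refers to the other.

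**The case against.** The strongest reply is that the table can be decoded. Negative critical points and two rows that fit only one-sided normal tails identify its scale and tail, so t-score is a wording slip. The sentence that introduces the table points to the alpha column as the criterion, and 0.00122 is the correct value there, which reduces look 2 to one digit. A balance check and efficacy looks can also coexist.

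Most of this stands, and it limits the size of the point. It does not remove it: the decoding is inference, the two columns still conflict, and the sample size points to the other sidedness.

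Several stronger readings are tempting and are not supported:

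- *The final row is wrong and should be -2.413.* Not shown. With binding futility, -2.406 holds the level. The gap between 0.00806 and 0.00804 is trivial.
- *The final bound can be read from the table as 2.65.* It cannot. That value arises only if two-sided .0083 was intended and the table is recomputed.
- *N is therefore two-sided.* Section 8.1 states neither what SD 30 refers to nor a Wilcoxon factor, so this remains an inference.
- *The look timing is inconsistent.* Section 8.5 calls the counts approximate, and a spending function allows bounds to be recomputed at the actual information.

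**Conclusion.** The point holds, at the level of something that should be fixed before the first look. Three things are established from the documents: the look-2 critical value and alpha do not match on any scale as printed; the text and table name different scales and no section states sidedness; and the Synopsis and Section 8.5 give the looks different purposes. The text reviewed was machine-read from the PDF, so the -3.09 should first be checked against the original page. The scale, sidedness and Synopsis points do not depend on that digit.

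The numerical effect is small. A reader might infer material type I error inflation or an underpowered study, and neither follows: one-tail error is about 0.0084 against .0083, and 119 gives about 80% fixed-design power on the two-sided convention and more on the one-sided. Those power figures rest on SD 30 being the SD of the paired difference, the pi/3 factor and independent target areas, although a participant may contribute two.

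**What to change.** Before any interim look:

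1. State one sidedness in Sections 8.1 and 8.5, and replace t-score with Z in the text of 8.5.
2. If one-sided .0083 on the Z scale is confirmed, correct the look-2 critical point to -3.03 to match 0.00122, and restate the fixed-design power in 8.1 as about 87% under the assumptions above. Leave the final row at -2.406, which is consistent with the futility rule if that rule is binding. About -2.413 is a conservative option only if futility is declared non-binding.
3. If two-sided .0083 was meant, recompute the whole table: about +/-4.81, 3.31 and 2.65 at 40, 80 and 119, with power about 80%.
4. In Section 8.9, refer to the final level in 8.5 for the VAS pain contrast that sized the study, so that the general .05 is not applied to it.
5. Reconcile the Synopsis note with 8.5: say whether the balance check, the efficacy and futility tests, or both apply, and that the trial may stop early.

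The cost is a corrected table and a few sentences, with no extra participants. Choosing two-sided makes the final bound stricter. By simulation under the sizing assumptions, it lowers power with the looks from about 86% to 80% and the chance of crossing by look 2 from about 41% to 30%.

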8.6. Endpoints

8.6.1. Primary Endpoints

1. Improvement in skinfold conditions such as erythema, maceration, denudation, and satellite lesions, which will be rated on Likert scales by a third-party clinician using photographs taken by the PI or qualified designee on Days 0, and Days 1, 3, and 5 (or last day of study participation [ie, fully healed target area(s)]) during SPT changes.
2. PI or qualified designee evaluate the odor of the target area(s) using a Likert scale on Days 0, and Days 1, 3, and 5 (or last day of study participation [ie, fully healed target area(s)]) during SPT changes.
3. Participants evaluate the discomfort in their skin fold: pain, itching, or burning using VAS survey on Days 0, and Days 1, 3, and 5 (or last day of study participation [ie, fully healed target area(s)]) during SPT changes, and report the most prominent type of discomfort (pain, itching, or burning) in their target area(s).

8.6.2. Secondary Endpoints

1. PI or qualified designee assess moisture in the target area(s) on Day 0, and on Days 1, 3, and 5 (or last day of study participation [ie, fully healed target area(s)]), during SPT changes, using a Likert scale.
2. HCPs report their feedback about the SPT on Day 5 (or last day of study participation [ie, fully healed target area(s)]), using VAS survey.
3. Participant report their experience with the SPT on Day 5 (or last day of study participation [ie, fully healed target area(s)]), using VAS survey.

8.7. Demographics, Variables and Covariates

Age will be collected as a continuous measure, with all participants being ≥ 18 years of age. Age will be considered for secondary analysis.

Sex will be collected as a categorical variable equal to 0 = male, 1 = female, or 2 = other. Sex will be considered for secondary analysis.

Ratings for erythema, maceration, denudation, satellite lesion, odor, and survey responses for moisture in the target areas with skinfold conditions, obtained using Likert scales, will be evaluated as categorical measures. Survey responses for discomfort, HCP feedback and participants' overall experience obtained on a VAS (1–100mm) will be evaluated as continuous measures.

Nominal variables of data collected will include the participant ID, medical history, and concomitant medications. Additional nominal information regarding date, time, and reason for additional SPT changes will be recorded in a log file and this data will be incorporated into supplemental analyses examining if results differ for participants with additional SPT changes.

8.8. Missing Data

All attempts will be made to collect all data per protocol. Any data point that appears to be erroneous or inexplicable based on clinical judgement will be investigated as a possible outlier. In general, values for missing data will not be imputed unless methods of handling missing data are specified in this section or relevant sections.

For the analyses of all primary and secondary objectives, observations with missing clinical ratings (ie, rating of erythema by a third-party clinician) or self-reported ratings (ie, VAS score of participant experience) will be dropped from the analysis of variable of interest.

All missing data will be quantified in the final report and possible biases for any missing data will be reported.

8.9. Statistical Analysis

Statistical analyses will be conducted in SAS[®] software, Version 9.4 or higher of the SAS System for Windows (Copyright © 2013 SAS Institute Inc.) or other appropriate statistical software. A p-value of $P < .05$ will be considered statistically significant.

All continuous variables will be summarized using the following descriptive statistics: (non-missing sample size), mean, standard deviation, median, maximum and minimum. The frequency and percentages (based on the non-missing sample size) of observed levels will be reported for all categorical measures. In addition, 95% confidence intervals will be calculated for all means.

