8.9.1 Analysis of Primary Endpoints

The primary goal of this study is to evaluate the efficacy of the SPT to improve skinfold conditions, including erythema, maceration, denudation, satellite lesions, pain, itching, burning and odor over five days of treatment. Erythema, maceration, denudation, satellite lesions, and odor will be assessed using Likert scales, with "0" being least severe and "4" being most severe. Ordinal mixed models, or other appropriate methods depending on the distribution of data, will be employed to compare the assessment of skin fold

conditions of target areas across five days of treatment, with participants as a random variable and treatment days (Day 0, and Days 1, 3, and 5) as a covariate. Significant omnibus test will be followed by Tukey's post-hoc pairwise comparisons of Day 0 vs Day 1, Day 0 vs Day 3, Day 0 vs Day 5, Day 1 vs Day 3, and Day 3 vs Day 5.

ANOVA/Mixed models, or other appropriate methods depending on the distribution of data, will be conducted to compare VAS scores of discomfort (pain, itching, or burning) reported by participants on Day 0, and Days 1, 3, and 5. Significant omnibus test will be followed by Tukey's post-hoc pairwise comparisons of Day 0 vs Day 1, Day 0 vs Day 3, Day 0 vs Day 5, Day 1 vs Day 3, and Day 3 vs Day 5. In addition, descriptive statistics for the most prominent discomfort in the target area will also be reported in this study.

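### Section 8.9 tests eight (or six) primary outcomes at .05 each with no error control or success rule across them, and never connects to the .00804 final level in Section 8.5

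*Combined protocol and SAP*

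**What the plan says.** Section 8.9 sets the only threshold in the analysis section: "A p-value of $P < .05$ will be considered statistically significant". It names no outcome and no look.

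Section 8.9.1 states the primary goal as improvement in skin fold conditions, "including erythema, maceration, denudation, satellite lesions, pain, itching, burning and odor over five days of treatment". That is eight outcomes. Section 6.2.1.3 can be read as a single discomfort mark on one VAS, which would make it six. The error control is described per outcome: "Significant omnibus test will be followed by Tukey's post-hoc pairwise comparisons", with five day pairs listed.

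Section 8.1 sizes the study on VAS pain, for a difference of 10 "between days of SPT changes with an estimated standard deviation of 30 and a Bonferroni adjusted" alpha of .0083 at 80% power. It names neither the day pair nor the sidedness, and does not say which six tests the Bonferroni divisor covers.

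Section 8.5 plans two looks "testing for early efficacy or futility" and says "the nominal alpha levels to reject the null hypotheses for efficacy are as follows in the table below". The table ends with Z = -2.406 and alpha 0.00804 at 119 target areas. Section 8.9 does not refer to this table. The note at the end of the Synopsis (Section 1.1) gives the looks another purpose: "Two interim analyses will be conducted to confirm that participants being enrolled present a balanced distribution of skin fold conditions".

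**The concern.** Tukey's procedure protects the family of day pairs inside one outcome. It does nothing about the other five or seven outcomes, each of which gets its own test at .05. Nothing says how many outcomes, or which, must improve for the primary objective to be met. One significant result out of eight could therefore be presented as success, and a reader could not say from the plan that this was wrong.

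For VAS pain, the outcome that set the sample size, there is a second problem. Two final criteria are on the page, Tukey-adjusted .05 in Section 8.9 and .00804 in Section 8.5, and the plan does not say which decides. Nor is it settled whether efficacy looks happen at all.

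**Working it through.** **Inputs.** From Section 8.1: difference 10, SD 30, alpha .0083, 80% power, 119 areas, paired Wilcoxon. From Section 8.5: looks at 40, 80 and 119 areas; Z = -4.42, -3.09, -2.406; final alpha .00804. From Sections 8.9 and 8.9.1: .05, four assessment days, five listed pairs, eight or six outcomes. Assumed, because the documents do not give them: correlations between outcomes, and independence of target areas.

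**1. The plan's own sample size.** The effect is 10/30 = 0.333. A paired t test at two-sided .0083 needs 113 areas for 80% power. Allowing for the Wilcoxon test's relative efficiency of 3/π, 113 × π/3 = 118.3, so 119. The stated N is reproduced. With .0083 one-sided the same method gives only 102–103, so Section 8.1 is using .0083 two-sided.

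**2. The Section 8.5 boundaries.** P(Z < -2.406) = .00806 one-sided (.0161 two-sided), so the printed .00804 is a one-sided level. The chance of crossing any of the three printed boundaries under the null is .00835 one-sided. That is the .0083 of Section 8.1, now spent one-sided. The match points to VAS pain as the intended outcome. The contrast remains unnamed.

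**3. Is leaving .0083 out of Section 8.9 an error in itself?** Four assessment days give 4 × 3/2 = 6 pairs, and .05/6 = .0083. Tukey at .05 with 4 days and 354 degrees of freedom has q = 3.650, so t = 3.650/√2 = 2.581 and an unadjusted per-pair P of .0102. A six-pair Bonferroni has t = 2.653. The two do roughly the same job within one outcome. The gap lies across outcomes.

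**4. Error across outcomes.** Null data were simulated for 119 independent areas on 4 days. A false improvement was counted when a repeated-measures ANOVA omnibus test (standing in for the ordinal model) reached .05 and at least one listed Tukey pair was significant in the improving direction. The rate per outcome is about .02. By hand, under independence: 1 - .98^8 = .149 and 1 - .98^6 = .114. Simulated, normal data:

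| Correlation between outcomes | 0 | .3 | .5 | .7 |
|---|---|---|---|---|
| Eight outcomes | .146 | .134 | .114 | .090 |
| Six outcomes | .111 | .105 | .092 | .075 |

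Replacing five outcomes by 0–4 Likert scores with half the values at zero gives .147 to .098 (eight) and .112 to .081 (six). If only four of the eight outcomes are truly unchanged, the figure is .055 to .077.

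**5. Power for VAS pain at 119 areas.** Effective n = 119 × 3/π = 113.6, and noncentrality = 0.333 × √113.6 = 3.553. This treats areas as independent and ignores interim looks.

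| Level | Power |
|---|---|
| One-sided .00804 (Section 8.5) | 86.4% |
| Two-sided .0102 (current Tukey per-pair level) | 82.4% |
| Two-sided .0083 (= .05/6) | 80.5% |
| Two-sided .00625 (= .05/8) | 77.6% |

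**The case against.** The authors could answer that the Bonferroni level in Section 8.1 is the multiplicity control. As written it belongs to VAS pain between days, and Section 8.9 does not carry it over. Applied to each of eight outcomes it would still sum to 8 × .0083 = .066; only with six does it sum to .0498.

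They could say that Section 8.5 governs the final test, and that its link to VAS pain is clear from the matching .0083 and from the reference to the original design in the futility rule. The inference about the outcome is reasonable and is accepted here. The contrast and the sidedness cannot be inferred, and the sidedness conflicts with Section 8.1.

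They could also say that counting eight is one reading among several: the Synopsis numbers one primary endpoint with three parts, and Section 8.6.1 lists three. That is fair, but neither layout comes with a testing rule, and Section 8.9.1 analyses the conditions outcome by outcome.

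Finally, this is a post-market, unblinded, single-arm study in which healing before Day 5 is expected, so a null in which nothing changes is unlikely. That limits the practical weight of the error rates. It does not remove the need for a success rule in a plan with a primary efficacy objective, a powered sample size and spending boundaries.

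A reader might infer a false-positive rate of 33.7% (1 - .95^8) or 26.5% (1 - .95^6). Those figures count worsening, and omnibus rejections with no improving pair, under independence. They do not measure false improvement. A reader might also infer that dropping .0083 from Section 8.9 is itself a mistake; step 3 shows that Tukey largely replaces it.

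**Conclusion.** The point holds. Section 8.9 applies .05 to each of eight (or six) primary outcomes, controls error only within an outcome, and no section defines success across them. If no outcome changes, the chance of at least one false improvement is about 9–15% over eight outcomes and 7–12% over six. These figures rest on independent target areas, the ANOVA stand-in and correlations of .7 to 0.

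The levels in the plan also do not fit together. The .00804 of Section 8.5 probably concerns VAS pain, but it has no named outcome or contrast and no link to Section 8.9. The .0083 behind it is one-sided there and two-sided in the sample size. The Synopsis and Section 8.5 disagree on what the interim looks are for.

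The documents do not support the stronger inference that efficacy looks will certainly take place and add to the error, since the Synopsis describes them only as checks of balance. Nor do they show that 119 areas is too few; the power can be restated instead.

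**What to change.** 1. State whether discomfort is one VAS score or three.
2. For the primary outcomes, replace the .05 sentence with one rule that holds overall two-sided error at .05. Three options:
   - Holm across the outcomes' omnibus tests, keeping the planned Tukey pairs. This changes least. If claims on individual day pairs are to be covered as well, run Tukey at .05 divided by the number of outcomes.
   - Holm across outcomes on Day 0 versus Day 5 (or last day of participation).
   - VAS pain as the single primary outcome, with the rest supportive. This narrows the claim, because Section 5.1 lets areas be enrolled without pain.
3. Reconcile the Synopsis note with Section 8.5. If efficacy looks remain, name the outcome, contrast and sidedness they govern and recompute the boundaries from that outcome's alpha share. Test each other outcome once with the remaining alpha, at 119 areas or at the stopping look if the trial stops early. With O'Brien-Fleming-type spending at 40, 80 and 119 areas, the boundaries are about Z = -4.96, -3.42, -2.75 for a two-sided share of .00625; -4.81, -3.31, -2.65 for .0083; and -3.69, -2.50, -1.99 for .05. Futility is taken as non-binding, because Section 8.5 says only "then the trial will be considered for stopping".
4. Cross-reference Sections 8.1, 8.5 and 8.9, and restate power at the chosen level rather than enrol more.

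**Cost.** SAP wording, new boundaries if looks remain, and a restated power figure. The six-outcome rule keeps the stated 80% (80.5%), but gives up about 2 points against the current Tukey level (82.4 - 80.5) and about 6 against one-sided .00804 (86.4 - 80.5). With eight outcomes power is 77.6%. Two areas per participant and re-enrolment would lower these figures if areas are correlated. None of this addresses the lack of a control arm: a significant change from Day 0 could still reflect natural course or other care.

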4.2. End of Study Definition

The study will be considered complete after the participants are dismissed upon completion of all study-related activities, the third-party clinician has assessed 119 target areas, and a Clinical Study Report approved by the Clinical Affairs Director has been issued.

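### The plan does not settle whether the interim looks can stop the trial for efficacy; if they can, the ordinary mean is biased after a stop, and the final 95% interval does not match the final boundary

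*Combined protocol and SAP*

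**What the plan says.** Section 8.5 (Interim Analysis) states: "Two interim analyses will be performed at 34% and 67% completion, testing for early efficacy or futility". It places the looks as follows: "the two interim analyses will occur after approximately 40 (1/3 of 119 total target areas) and 80 (2/3) target" areas. It tabulates critical Z-values for rejecting the null for efficacy of -4.42 (40 areas), -3.09 (80) and -2.406 (119, nominal level 0.00804). It speaks of stopping only for futility, and it names neither the endpoint nor the pair of days being tested.

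Two other places point elsewhere. The note closing the synopsis (1.1) gives the purpose of the two looks as confirming a balanced mix of skin fold conditions. Section 4.2 makes completion depend on several things, one being that "the third-party clinician has assessed 119 target areas", with no provision for an early stop. Sections 5.4 and 8.1 also recruit to 119.

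On estimation, section 8.9 sets P < .05 as the significance criterion and says "95% confidence intervals will be calculated for all means". Section 8.9.1 adds mixed models with Tukey comparisons between days. No section gives an estimate or interval adjusted for the looks.

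**The concern.** A trial that stops because its interim mean crossed a boundary has selected a high value. The unadjusted mean then overestimates the change on average, and its usual interval is off-centre. If 8.5 means what its efficacy boundaries suggest, the plan gives no estimate suited to that outcome. If 4.2 governs and enrolment always runs to 119, this problem does not arise, but then the consequence of crossing an efficacy boundary is undefined. Either way, the choice should not be made after the interim data are seen.

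A second mismatch needs no early stop. A reader of the final report will see a 95% interval and a P < .05 criterion, while 8.5 rejects only beyond Z = -2.406. The same result could be presented as positive by one section and not by the other.

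**Working it through.** **Inputs.** From 8.1: "minimal clinically significant difference of 10 in the VAS pain scale", "with an estimated standard deviation of 30", Bonferroni alpha .0083, 80% power, N = 119. From 8.5: looks at 40, 80 and 119, with Z = 4.42, 3.09 and 2.406 (improvement taken as positive). Assumptions not in the plan: SD 30 is the SD of the paired differences, differences are normal, target areas are independent, and the tested contrast is a VAS change.

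**The plan's own figures.** A paired-test power calculation with the Wilcoxon efficiency factor π/3 and two-sided .0083 gives N = 118, and power at 119 is 80.5%. So 119 is reproduced. The three printed Z-values together spend 0.00835 one-sided, so the boundaries are one-sided while the sample size matches a two-sided test. The printed 0.00122 at the second look corresponds to Z = 3.03; Z = 3.09 corresponds to 0.00100.

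**Smallest mean change that crosses, Z × SD/√n.**
- 40 areas: 4.42 × 30/√40 = 21.0 mm
- 80 areas: 3.09 × 30/√80 = 10.4 mm

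Both exceed the 10 mm design value, so under these assumptions every early efficacy stop reports more than the effect the trial was sized for.

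**Chance of a stop at a true 10 mm.** The expected Z at 40 areas is (10/30)√40 = 2.11, so P(Z > 4.42) is about 1.0%. At 80 areas the expected Z is (10/30)√80 = 2.98, just under 3.09. A further 44.6% stop there, giving 45.6% in all.

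**Estimate after a stop** (2 million simulated trials per row, known SD, ordinary mean at the stopping look):

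| True change (mm) | Stop early | Mean estimate given stop (mm) | Bias given stop | Bias over all trials | 95% coverage given stop |
|---|---|---|---|---|---|
| 5 | 5.5% | 11.85 | +137% | +2.6% | 54% |
| 7.5 | 19.7% | 12.3 | +64% | +4.3% | 87% |
| 10 | 45.6% | 13.05 | +31% | +5.0% | 93% |
| 12.5 | 74% | 14.2 | +14% | +4.4% | 95% |
| 15 | 92% | 16.0 | +7% | +4.0% | 96% |

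At 10 mm, a stop at 80 areas alone carries +28%. A stop at 40 areas carries +126%, but happens in about 1% of trials. With a t statistic and Z = 3.03 at the second look the combined figure at 10 mm is 29%; with a Wilcoxon statistic it is 32%.

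**Final look, 119 areas.** The standard error is 30/√119 = 2.75 mm.
- The 95% interval excludes zero from 1.96 × 2.75 = 5.4 mm.
- The 8.5 boundary rejects from 2.406 × 2.75 = 6.6 mm.

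A result falls between the two in about 6% of trials at a true 10 mm, 15% at 7.5 mm and 16% at 5 mm.

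**Source of that gap.** One-sided .0083 with no looks already gives Z = 2.395. The looks move this only to 2.406. Against the distance from 1.96, that is (2.406 − 2.395)/(2.406 − 1.96) = 0.011/0.446, about 2%.

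**P < .05.** For a single unadjusted two-sided contrast this means |Z| > 1.96. If P is Tukey-adjusted over the four assessment days, the large-sample critical value is 3.633/√2 = 2.57, or 7.1 mm. Neither equals 2.406.

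**The case against.** The strongest reply is that an early efficacy stop is not clearly planned: 8.5 uses stopping language only for futility, the synopsis gives the looks a different purpose, and 4.2, 5.4 and 8.1 all aim at 119. That stands, and it is why reconciling these sections comes first. It does not remove the point, because 8.5 prints values for rejecting the null early and leaves the consequence open.

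A reader might infer that any early stop inflates the result by 30% or more. The plan does not support this. The 10 mm in 8.1 is a minimal clinically significant difference, not a forecast. Above it the bias shrinks while early stops become more common.

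A reader might also infer that the 95% interval fails badly after any stop. At 10 mm its coverage given a stop is 93%. It is poor mainly when the true change is well below 10 mm or after the rare stop at 40 areas.

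Nor should the gap between 1.96 and 2.406 be blamed on the interim looks; it is almost wholly the Bonferroni level taken one-sided, and a fixed design would show it too.

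Finally, the interval sentence in 8.9 sits among descriptive summaries, primary inference is in 8.9.1, and five of the primary conditions are ordinal ratings to which millimetre figures do not apply. That limits the numbers to a VAS contrast. But 8.9 contains the only interval the plan specifies, and it covers all means.

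**Conclusion.** The point holds in a conditional form. The plan must say whether crossing an efficacy boundary ends the trial. If it does, the ordinary mean overstates the contrast that triggered the stop. At the plan's own 10 mm and SD 30 the excess is about 31% in the 46% of trials that stop early, and about 5% over all trials. The size depends on the unknown true change and on normal differences and independent areas; the plan allows two areas per participant and re-enrolment, so independence is an approximation. The figures do not carry over to the Likert ratings or to variables that did not trigger the stop.

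The mismatch between the 95% interval and the final boundary does not depend on that answer. It covers mean changes of 5.4 to 6.6 mm at 119 areas. Whether P < .05 also conflicts in that range depends on whether P is Tukey-adjusted, but it does not match the 8.5 level in either case.

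**What to change.** 1. Reconcile the synopsis note, 4.2 and 8.5 on the purpose of the looks and on what follows a crossed efficacy boundary. In 8.5, name the endpoint, the day contrast and the test statistic used at the looks. The remaining steps depend on this.
2. Choose one of two routes. Either state that the looks cannot stop the trial for efficacy and that enrolment continues to 119; or state in 8.9 that after an efficacy stop an estimate and interval adjusted for the sequential design are reported beside the ordinary mean for that contrast. A median-unbiased estimate with a stage-wise-ordering interval is one suitable choice among several. The second route also needs an early-stop provision in 4.2.
3. For the tested primary contrast, replace P < .05 with the 8.5 level and say whether Tukey adjustment still applies to it. Give its final interval at the matching level: one-sided 0.00804 corresponds to a two-sided interval of 1 − 2 × 0.00804 = 98.4%.

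No extra participants or data are needed. The work is a short set of edits to the synopsis, 4.2, 8.5 and 8.9, plus the decision on the tested contrast. The price is a somewhat smaller estimate after an early stop and a wider final interval (half-width 6.6 mm instead of 5.4 mm at SD 30).
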